### Effect measures

The effect measures for pooling are the study site-specific IVE estimates and their 95% confidence intervals (CIs).

## Sample size considerations

[Sample size considerations for the primary objective(s) should be discussed in this section including the assumptions made for vaccination coverage, vaccine effectiveness and influenza attack rate. This section will be updated pending consultation with the DRIVE Ethics Advisory Board and EMA on the need to establish minimum sample size and/or minimum precision for the primary objective(s)].

## Strategy for data synthesis

#### Inclusion criteria

We will pool seasonal IVE estimates from the individual study sites in line with the objectives as per study protocol (Section 3.1). Estimates that are not obtained following the study protocols will not be retained for the primary meta-analysis, but might be considered for inclusion as part of a sensitivity analysis (Section 3.4.6). Whenever there are two or more site-specific estimates retained, a meta-analysis will be performed.

as per study protocol) might be considered upon lack of heterogeneity (see Sections 3.4.4 and 3.4.5).

#### **Meta-analysis**

For every objective listed in Section 3.1, a meta-analysis will be performed. First, the study sitespecific IVE estimates will be back-transformed to the original relative risk (RR) estimates (in case of cohort studies) and odds ratio (OR) estimates (in case of case-control studies), which will be subsequently log-transformed, or

 $\log RR \text{ or } \log RR = \log(1-VE)$ 

Then, standard inverse variance weighted random-effects meta-analysis of the log-transformed RR and OR estimates will be used to obtain the pooled estimate (2). The pooled estimate (and 95% CI) will then be back-transformed to obtain the pooled IVE estimate (and 95% CI), expressed in %.

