## Sample size considerations

This section gives sample size considerations and formulates recommendations. These recommendations are meant to support the design of the case-control studies on IVE. Obtaining a minimum sample size is not a requirement for study participation. Details on the sample size calculations based on the minimal detectable VE as well as precision are given in Annex 3.

DRIVE recommends case-control studies based on 500 cases or more. However, studies with smaller sample sizes might still contribute to the power of the pooled analyses, provided that the study site is able to optimally harmonise its protocol with the other study sites to minimize the

between-study heterogeneity. In case VE estimates with unacceptable large CIs are obtained, it might be considered to not report these estimates.

Figure 1 presents the precision of the overall VE for number of cases varying from 200 to 4000 subjects, when assuming a true VE of 50%, a 'cases to controls' ratio of 1:1 and a total vaccination coverage of 5%, 20%, 50% and 70%. The number of cases per control is likely to vary (by definition of test-negative design). The calculations are based on an anticipated true VE of 50% as this is a conservative choice, requiring larger sample sizes compared to assuming lower/higher VE values. A case-control study based on 500 cases and a 1:1 'cases to controls' ratio will result in 95% CIs of the overall VE with a lower limit larger than 30% given a true VE of 50%, for coverages of >20%.

**Figure 1.** Precision of the overall VE expressed as the lower limit of the 95% CI, assuming a true VE of 50%, a 'cases to controls' ratio of 1:1 and a total vaccination coverage of 5%, 20%, 50% and 70%.

Figure 2 presents the precision of the brand-specific VE for number of cases varying from 200 to 4000 for the same parameter settings as above and additionally assuming the brand of interest accounts for 10%, 20%, 40%, 60%, 80% and 90% of the total vaccination coverage. A case-control study based on 500 cases and a 1:1 'cases to controls' ratio will result in 95% CIs of the brand-specific VE with a lower limit larger than 25% given a true VE of 50%, for brands covering 40% to 90% of the influenza vaccines when the overall vaccination coverage is 50% or more.

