#### Measure of effect

The crude (or unadjusted) brand-specific IVE will be estimated as

$$VE = (1 - OR) \times 100\%$$
,

where *OR* denotes the odds ratio, comparing the odds of vaccination among influenza-positive study participants by the odds of vaccination among influenza-negative study participants. The 95% confidence intervals will be obtained as well.

Confounder-adjusted brand-specific IVE estimates will be obtained from multivariable logistic regression models, regressing the health outcomes of interest on exposure status, age, sex and the confounders of interest. In case of effect modifiers, an interaction term between exposure and the effect modifier will be included in the regression model or stratified regression analyses will be performed.

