## **Precision**

The precision refers to the level of sampling error. The standard error and consequently the width of confidence intervals (CI) are measures of precision. As the VE CIs are asymmetric, we express precision as the lower limit of the two-sided CI of the anticipated true VE, expressed in %. The precision can be derived starting from the anticipated true VE, the confidence coefficient  $(1 - \alpha/2)$ , the number of cases, the 'cases to controls' ratio 1:*r* and the overall vaccination coverage  $\gamma$ . Consider the notation as defined in Table 1, where *N* is the total number of subjects,  $N_d^+$  the number of cases,  $N_d^-$  the number of controls,  $N_e^+$  the number of vaccinated subjects,  $N_e^-$  the number of unvaccinated subjects and where *r* is the number of controls per case and  $\gamma$  is the coverage.

Table 1: Cross-tabulation of	f exposure a	and disease in a	case-control study
------------------------------	--------------	------------------	--------------------

	Diseased				
		Yes (cases)	No (controls)		
Exposed	Yes	a	b	$N_e^+ = N \gamma$	
	No	С	d	$N_e^- = N(1 - \gamma)$	
		$N_d^+$	$N_d^- = r N_d^+$	N	

Then, from the lower limit of the CI for VE estimates based on a case-control study, or

$$VE_{LL CI} = 1 - exp \left[ \log(OR) + Z_{\alpha/2} \sqrt{\frac{1}{a} + \frac{1}{b} + \frac{1}{c} + \frac{1}{d}} \right],$$
(3)

where OR = 1 - VE and where  $Z_{\alpha/2}$  is the standard normal z-score, it follows that the precision is determined for given values for *a*, *b*, *c* and *d*. From anticipated values for *OR*,  $N_e^+$ ,  $N_e^-$  and  $N_d^+$ , the

cell count a can be analytically derived as;

$$a = \left(\frac{1}{2}\right) \sqrt{\frac{x_1 + x_2 + x_3}{(OR - 1)^2}} + \frac{N_e^+ OR + N_e^- + N_d^+ OR - N_d^+}{2(OR - 1)},$$
  

$$b = N_e^+ - a$$
  

$$c = N_d^+ - a$$
  

$$d = N_d^- - b$$

where  $x_{1} = N_{e}^{+2} OR^{2} + 2N_{e}^{+}N_{e}^{-}OR - 2N_{e}^{+}N_{d}^{+}OR^{2} + 2N_{e}^{+}N_{d}^{+}OR$   $x_{2} = N_{e}^{-2} + 2N_{e}^{-}N_{d}^{+}OR - 2N_{e}^{-}N_{d}^{+}$   $x_{3} = N_{d}^{+2}OR^{2} - 2N_{d}^{+2}OR + N_{d}^{+2}$ 

We calculated the precision of the overall VE based on a two-sided 95% CI for case-control studies using 'cases to controls' ratio of 1:1, 1:2 and 1:4 with the total number of cases varying from 100 to 4000, while assuming overall vaccination coverages of 5%, 20%, 50% and 70% and overall VE of 20%, 50% and 70%.

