We additionally calculated the precision of the brand-specific VE, where cases/controls are considered exposed when they were vaccinated with the brand of interest and unexposed when they were unvaccinated. This means that subjects vaccinated with another brand are excluded from the analysis and that the same comparator group of unexposed subjects is used for the different brand-specific estimates. The precision of brand-specific VE is calculated for case-control studies using a 'cases to controls' ratio of 1:1 using the same settings as above, additionally assuming that the brand of interest accounts for 10%, 20%, 40%, 60%, 80% and 90% of the overall vaccination coverage.

The results for precision of the overall VE using 'cases to controls' ratio of 1:1, 1:2 and 1:4 are given in Figure 3 to 5, respectively. These figures represent precision by number of cases. The results for the precision of brand-specific VE using 'cases to controls' ratio of 1:1 for anticipated true VE of 20%, 50% and 70% are given in Figures 6 to 8.

c) 70% VE

**Figure 3.** Precision of overall VE for a case-control study (1:1 case-control ratio) assuming overall vaccination coverage of 5%, 20%, 50% and 70%, and anticipated true VE of 20%, 50% and 70% (indicated with the black horizontal line), by number of cases.

c) 70% VE

**Figure 4.** Precision of overall VE for a case-control study (1:2 case-control ratio) assuming overall vaccination coverage of 5%, 20%, 50% and 70%, and anticipated true VE of 20%, 50% and 70% (indicated with the black horizontal line), by number of cases.

c) 70% VE

**Figure 5.** Precision of overall VE for a case-control study (1:4 case-control ratio) assuming overall vaccination coverage of 5%, 20%, 50% and 70%, and anticipated true VE of 20%, 50% and 70% (indicated with the black horizontal line), by number of cases.

**Figure 6.** Precision of brand-specific VE for a case-control study (1:1 cases to controls ratio) assuming an anticipated true VE of 20% (indicated with the black horizontal line), overall vaccination coverage of 5%, 20%, 50% and 70% with the brand of interest covering 10%, 20%, 40%, 60%, 80% and 90% of the overall coverage, by number of cases.

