# BACKGROUND

The DRIVE consortium aims to enable the collaboration of different public and private stakeholders to perform annual brand-specific influenza vaccine effectiveness (IVE) studies for various influenza vaccines on the European market. To this end, IVE studies will be conducted at various study sites across Europe. In a second step, the site-specific data will be combined to obtain overall estimates at the European level. The purpose of this document is to provide guidance for writing the Statistical Analysis Plan (SAP) of combining and presenting information on IVE from different study sites. This document will be updated following the learnings from the pilot year 2017-2018.

There are two statistical approaches for pooling data: a one-stage or a two-stage pooling approach (1). The two-stage approach refers to the classical meta-analytical approach, also called aggregated data meta-analysis (AD-MA). In this approach, the patient-level or minimally aggregated data from each study are analysed separately in order to obtain the effect estimates of interest (here vaccine effectiveness estimates) and the corresponding confidence intervals (CIs). Then, in the second step, the effect estimates are combined by an appropriate meta-analysis model to obtain the meta-analytical (weighted averaged) estimate. The one-stage pooling approach analyses all the combined patient-level or minimally aggregated data from the different data sources in a single step. This approach is also called the individual participant data meta-analysis (IPD-MA).

We opt to pool data using the AD-MA approach, given the statistical equivalence of AD-MA and IPD-MA, given that many of the mentioned advantages of IPD-MA (i.e. transforming data to common sources or measures and standardizing analysis) can also be achieved through harmonization/standardization of the individual site-specific studies and given the additional complexity of performing IPD-MA when data are collected using different study designs (1). Within AD-MA, we prefer the use of random effects meta-analysis model, which assumes that the observed effect estimates can vary across study sites because of differences in the treatment effect in each study site (e.g. due to differences in population, in health care utilization, in circulating influenza strains) as well as sampling variability.

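### The SAP's two-stage pooling rule has no provision for sites with a zero cell, and pulls brand-specific pooled VE toward zero when brand-vaccinated cases per site are few

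*Combined protocol and SAP*

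**What the plan says.** SAP section 3.2 (Effect measures) names the site IVE estimates and their 95% CIs as the quantities to be pooled. Section 3.4.2 converts each to log(1-VE), and "standard inverse variance weighted random-effects meta-analysis of the log-transformed RR and OR estimates will be used to obtain the pooled estimate". Pooling needs very few sites: "Whenever there are two or more site-specific estimates retained, a meta-analysis will be performed" (section 3.4.1). SAP section 1 prefers the two-stage approach "given the statistical equivalence of AD-MA and IPD-MA", among other reasons.

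At site level the protocol (Measure of effect) says: "Confounder-adjusted brand-specific IVE estimates will be obtained from multivariable logistic regression models". No exact or penalised version is mentioned. For the brand-specific calculations in Annex 3, "subjects vaccinated with another brand are excluded from the analysis", so each brand's table holds only recipients of that brand and the unvaccinated.

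The protocol recommends 500 or more cases but sets no minimum, and says that "studies with smaller sample sizes might still contribute to the power of the pooled analyses". Annex 3 works with 100 to 4000 cases, coverage down to 5% and brand shares down to 10%. I found no continuity correction, minimum count of vaccinated cases or other zero-cell rule in either document.

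**The concern.** The primary objective puts brand first, and brand tables are the sparsest ones that the pooled analysis will use. If no influenza case at a site received the brand, OR = 0, VE = 100% and log(1-VE) does not exist. If no control received it, the log odds ratio is infinite in the other direction. The rule cannot use either site, so the analyst must decide what to do after seeing the data.

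The two losses do not balance. When the vaccine works, zero-case sites are more frequent than zero-control sites. Among the sites that remain, those with fewer vaccinated cases by chance show higher VE and also have larger variance and lower weight. Both mechanisms pull pooled VE toward zero. The pull is stronger for low-share brands and for more effective ones, so two brands with the same true VE could receive different pooled estimates because of market share.

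**Working it through.** **Inputs from the documents.** Pooling scale and weights: SAP 3.4.2. Variance of the log odds ratio: 1/a + 1/b + 1/c + 1/d (Annex 3, formula 3). Coverage: Annex 3 Table 1 defines it over cases and controls together, so vaccinated subjects = N × coverage. Grid of cases, coverage, brand share and VE: Annex 3.

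**Assumptions.** The documents do not give the number or mix of sites per brand. The main runs use six equal sites, a 1:1 ratio, no heterogeneity and DerSimonian-Laird pooling (the cited method), with zero-cell sites left out because the rule gives them no value.

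**1. The plan's own figure.** With 500 cases, 1:1, OR 0.5 and 20% coverage, the vaccinated margin is 1000 × 0.20 = 200. Solving a(500 - 200 + a) = 0.5(200 - a)(500 - a) gives a = 72.8, b = 127.2, c = 427.2, d = 372.8. The standard error is 0.163, so the lower limit is 1 - 0.5 × exp(1.96 × 0.163) = 31.2%. At 50% and 70% coverage it is 35.7% and 34.1%. The stated limit above 30% is reproduced.

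**2. What a zero cell does.** With a = 0, b = 4, c = 84, d = 80, the fitted log odds ratio is -11.6, -26.6 and -35.6 after 10, 25 and 50 iterations, and its standard error grows from 98 to 1.6 × 10^7. The site has no usable weight.

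**3. How often it happens (true VE 50%, Annex 3 coverage).** For 500 cases and 5% coverage the vaccinated margin is 50, and the same equation gives a = 17.04 and b = 32.96. For 200 cases and 20% coverage it gives a = 29.14.
- 500/5%/10%: 1.704 brand-vaccinated cases expected; P(none) = (1 - 1.704/500)^500 = 18%. For controls, 3.296 expected; P(none) = 3.7%.
- 500/5%/20%: 3.408 expected; P(none) = 3.3%.
- 200/20%/10%: 2.914 expected; P(none) = 5.3%.
- 500/20%/10%: 7.284 expected; P(none) about 0.1%.

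**4. Pooled VE, six equal sites, true VE 50% (medians).**

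| Cases/coverage/share | Annex 3 coverage | Coverage read as among controls |
|---|---|---|
| 500/5%/10% | about 39-40% | about 34-35% |
| 500/5%/20% | about 46-47% | about 44% |
| 200/20%/10% | about 46% | about 43-44% |
| 500/20%/10% | about 49% | about 49% |

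Mantel-Haenszel stratified by site, and a one-stage logistic model with site intercepts, gave 49-51% on the same sparse settings.

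At true VE 70% with Annex 3 coverage, the rule gives 64.8% (500/5%/20%) and 64.5% (200/20%/10%), a bias of about 5 points; at 500/5%/10% the bias is about 13-14 points.

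**5. Sensitivity.**
- Continuity correction: with 34.5% at 500/5%/10% (coverage among controls), adding 0.5 to zero-cell tables brings pooled VE only to 43.5%. In a five-site run (100 cases, 20% coverage among controls, 20% share), omitting zero-cell sites gave 42.8%, adding 0.5 to every table 43.1%, adding 0.5 to zero-cell tables only 46.7%, and Mantel-Haenszel 50.6%.
- Case-to-control ratio: in five-site runs at 500/5%/10% (coverage among controls), pooled VE was 35.2% at 1:1, 28.5% at 1:2 and 26.5% at 1:4. With more controls, zero-control sites almost vanish and the loss becomes one-sided.
- Heterogeneity: tau = 0.3 changed 35.2% to 32.6% in the same 1:1 setting.
- Site mix: three sparse sites (500/5%/10% or 200/20%/10%) with three at 500/20%/40% gave 49.2-49.3% at true VE 50% and 69.1-69.3% at 70%. Five sparse sites with one larger site left a bias of 2-4 points.

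**The case against.** Several counter-arguments carry weight.

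- The size is conditional. A reader might infer a general bias of 6-16 points from the control-coverage runs, or a 28% chance that a 500-case site has no brand-vaccinated case. Both read coverage as coverage among controls and both apply only to sparse settings. On Annex 3's definition the 28% becomes 18%, and at the recommended 500 cases with 20% coverage or more the bias is about 1 point or less.
- A reader might also infer that pooling loses exactly the most favourable sites. It does not: zero-control sites are lost too, and part of the bias comes from weighting the sites that stay. Nor do the documents say that zero-cell sites are dropped; they are silent, and omission is the practical result.
- Invalid intervals would be another overreading. In the sparse settings the 95% intervals covered the truth in about 93-98% of runs. At VE 50% the log-scale root mean squared error was no worse than for Mantel-Haenszel (0.46 against 0.48; 0.34 against 0.36). Such wide intervals might go unreported under the protocol's sample size section, although it sets no threshold.
- The SAP describes itself as guidance for writing an SAP, and its section 3.3 leaves minimum sample size or precision open. The protocol's Statistical analysis section already mentions one-stage pooling.

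These points limit the size and the severity. They do not remove the gap: section 3.4.2 is stated as a rule rather than a placeholder, and following it gives a systematic error whose size depends on brand share.

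**Conclusion.** The concern holds in conditional form. The pooling rule is undefined for a site with no brand-vaccinated case or no brand-vaccinated control, no zero-cell rule exists, and pooled brand-specific VE is biased toward zero when brand-vaccinated cases per site are few.

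The bias is about 3-11 points at true VE 50% in the three sparse settings examined, and about 5-14 points at true VE 70%. It is about 6-15 points at VE 50% if coverage is read as coverage among controls. It is negligible where counts are ample or where well-populated sites dominate. The figures rest on the assumed six equal sites, 1:1 ratio and no heterogeneity, none of which the documents fix. The equivalence of two-stage and one-stage pooling claimed in SAP section 1 does not extend to sparse data. Severity: should-fix.

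**What to change.** In SAP 3.4.2, pre-specify that for brands with sparse exposure the primary pooled VE comes from a one-stage logistic model on the Annex 1 patient records, with site-specific intercepts and the minimum-set covariates. Mantel-Haenszel stratified by site would serve for the crude estimate. Zero-cell sites stay in. Add a random vaccine effect only where the number of sites supports it. Report the two-stage result as a sensitivity analysis, and limit the equivalence statement in SAP section 1 to non-sparse data.

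The trigger should be a fixed threshold on total brand-vaccinated subjects per site, cases and controls combined. A trigger on the observed number of vaccinated cases would let the outcome choose the method. As a guide at 1:1, this total is 1000 × 5% × 10% = 5, 1000 × 5% × 20% = 10 and 400 × 20% × 10% = 8 in the three sparse settings, and 1000 × 20% × 10% = 20 where the bias is about 1 point or less. A threshold near 20 would separate them; other ratios need their own check.

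The cost is SAP wording, modest programming and not-estimable entries in the forest plot. No new data are needed, because Annex 1 already defines patient-level records for pooling. The covariate-adjusted model with a random vaccine effect was not simulated here and should be tested before it is adopted.

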#### Outlier and influence analysis

For every meta-analysis performed, the potential impact of outliers and influential estimates on the pooled estimate will be evaluated. Studentized deleted residuals *r* will be used to identify outliers in the meta-analysis. Site-specific IVE estimates will be considered outlying from meta-analysis when |r| > 2.5, where |r| indicates the absolute value of the residual (3).

The standardized DFBETAs statistic will be used to identify influential estimates, examining the change in the averaged IVE from the random-effects model when excluding one site-specific estimate in turn. Site-specific estimates will be considered influential from meta-analysis when  $|DFBETAs| > 2/\sqrt{n}$ , where where |DFBETAs| indicates the absolute value of the DFBETAs statistics and *n* is the number of effect estimates (3).

Site-specific estimates that are outlying and influential, will be excluded from meta-analysis and the reason for being outlying will be investigated and documented.

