#### Sensitivity analysis

Sensitivity analysis in line with the study protocol will be performed.

Additional sensitivity analyses will be performed by including site-specific estimates that were excluded from the main meta-analysis models because 1) they were not obtained following the study-protocol (Section 3.3.1) or 2) they were identified as outlying and influential (Section 3.3.3).

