#### **Presentation of results**

The site-specific IVE estimates (and 95% CIs) will be presented using a forest plot complemented with the pooled IVE estimate (and 95% CIs) as outlined in the report template. Estimates that were excluded from meta-analysis will included in the forest plot, but these estimates will be tagged as excluded. An example of a forest plot with pooled estimates by setting is given in Figure 1. This plot is generated using artificial data based on cohort designs.

Vaccinated Unvaccinated

	Vaccina	alcu	Uliva	comateu		
Study	Ν	n	Ν	n		Vaccine effectiveness % [95% CI]
Primary care FOR ILLUSTRATION ONLY: ARTIFICIAL DATA					ION ONLY: ARTIFICIAL DATA	
Country E	650	23	450	32		└───── ── 50.2 [ 16.1, 70.5]
Country D(3)*	1000	63	1000	70	μ	– 10.0 [-25.0, 35.2]
Country D(2)	3000	63	4000	280		→ 70.0 [ 60.7, 77.1]
Country D(1)	2500	61	2800	196		⊢■ 65.1 [ 53.8, 73.7]
Country C	500	21	500	35	H	40.0 [ -1.6, 64.6]
Country B	250	7	500	35		⊢−−−−− 60.0 [ 11.2, 82.0]
Country A	1200	42	1400	98		— 50.0 [ 28.8, 64.9]
Weighted average					52.49 [35.37, 65.07]	
(Heterogeneity	: 12 =77.19	%)				
Hospital						
Country F	1200	17	2400	168		⊢−−− 79.8 [ 66.8, 87.7]
Country E	400	7	500	35		→→→ 75.0 [ 44.3, 88.8]
Country A	800	17	780	55		▶ ● 69.9 [ 48.5, 82.3]
Weighted average					75.57 [66.01, 82.45]	
(Heterogeneity: 12 =0%)						
* excluded from pooled estimate because outlying and influential						
				Г 		
				-50	-12.5	25 62.5 100
Vaccine effectiveness %				ccine effectiveness %		

Figure 1: Forest plot and meta-analyses of influenza vaccine effectiveness, by health care setting. This plot is generated using artificial data based on cohort designs

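### The generic SAP's main meta-analysis drops protocol-compliant sites because of their own result, so the pooled interval is too narrow when sites truly differ

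*Combined protocol and SAP*

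**What the plan says.** The pooled analysis is a "standard inverse variance weighted random-effects meta-analysis of the log-transformed RR and OR estimates" (generic SAP, section 3.4.2). The SAP's Background prefers random effects because true effects may differ between sites through population, health care use and circulating strains.

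Section 3.4.3 sets two numeric criteria. For outliers: "Site-specific IVE estimates will be considered outlying from meta-analysis when |r| > 2.5", where r is the studentized deleted residual. For influence: "Site-specific estimates will be considered influential from meta-analysis when" the absolute DFBETAs statistic exceeds 2/√n. When both are met: "Site-specific estimates that are outlying and influential, will be excluded from meta-analysis and the reason for being outlying will be investigated and documented".

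Section 3.4.1 already keeps estimates not obtained under the protocols out of the primary meta-analysis, so the estimates that section 3.4.3 removes are protocol-compliant. Section 3.4.6 puts excluded estimates back only in additional sensitivity analyses, one reason being that "they were identified as outlying and influential". Section 3.4.7 keeps them in the forest plot, tagged. In the illustrative plot, Country D(3) carries the footnote "excluded from pooled estimate because outlying and influential".

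**The concern.** Exclusion comes first and the search for a cause second. No cause has to be found, and finding none does not restore the site. What triggers removal is that the site's VE lies far from the rest and moves the average.

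That conflicts with the SAP's reason for using random effects. If VE is expected to differ between sites, a distant site is part of the distribution being averaged. Deleting it lowers the estimated between-site variance and hence the standard error. It also lowers I², and a high I² is the SAP's prompt for exploring heterogeneity (section 3.4.4). At stake are the headline pooled estimate and its stated precision. Brand-specific VE is the protocol's first-listed primary aim, and pooling starts at two estimates (section 3.4.1), so meta-analyses with few sites are foreseeable.

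**Working it through.** **Inputs.** Vaccinated and unvaccinated counts for the seven primary care rows of the SAP's Figure 1 (artificial cohort data), and the thresholds of section 3.4.3. For n = 7 the influence threshold is 2/√7 = 0.756.

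**Site estimates.** With a/n₁ vaccinated and c/n₀ unvaccinated events, y = ln[(a/n₁)/(c/n₀)] and v = 1/a − 1/n₁ + 1/c − 1/n₀. For D(3), y = ln(0.063/0.070) = −0.105 and v = 1/63 − 1/1000 + 1/70 − 1/1000 = 0.0282. This gives VE 10.0% (−25.0 to 35.2), as printed. All seven printed rows reproduce.

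**The printed pooled line.** Weights are 1/(v + τ²), and the interval is the estimate ± 1.96 SE on the log scale. The plot prints "52.49 [35.37, 65.07" with I² 77.1%.

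| Sites pooled | Method | VE % (95% CI) | τ² | I² % |
|---|---|---|---|---|
| All seven | REML | 52.49 (35.37 to 65.07) | 0.124 | 77.1 |
| Without D(3) | REML | 59.12 (48.29 to 67.68) | 0.040 | 50.6 |
| All seven | DerSimonian-Laird | 52.43 (33.70 to 65.87) | 0.151 | 80.4 |
| Without D(3) | DerSimonian-Laird | 59.25 (48.84 to 67.55) | 0.036 | 47.6 |

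The printed line matches to the last digit only for REML with D(3) included, contrary to its footnote.

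**The rule applied to D(3)** (REML; leave-one-out mean ln(1 − 0.5912) = −0.894, SE 0.120, τ² 0.0404):

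- r = (−0.105 + 0.894)/√(0.0282 + 0.0404 + 0.120²) = 0.789/0.288 = 2.74, above 2.5.
- DFBETAs = (−0.744 + 0.894)/0.109 = 1.38, above 0.756. Here −0.744 = ln(1 − 0.5249), and 0.109 is the seven-site SE evaluated at the leave-one-out τ².
- No other site meets both criteria. DerSimonian-Laird gives 2.85 and 1.47 for D(3).

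**Effect.** VE rises by 59.12 − 52.49 = 6.6 points. The lower limit rises by 48.29 − 35.37 = 12.9 points. The interval width falls from 29.7 to 19.4 points, and the log-scale SE falls from 0.157 to 0.120 (−24%).

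**Beyond one example.** Simulation assumptions, not in the documents: true VE 50%, normal between-site variation with no aberrant sites, site SE of log OR 0.15 to 0.5, 4 to 10 sites, DerSimonian-Laird pooling, one pass of the rule.

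| Between-site SD (log OR) | A site is removed | Coverage, all sites | Coverage, rule applied |
|---|---|---|---|
| 0 | 3-8% | about 96% | 95-96% |
| 0.2 | 9-20% | 92-93% | about 89% |
| 0.4 | 24-33% | 88-91% | 78-84% |

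For scale, the example's between-site SD is √0.124 = 0.35 with D(3) and √0.040 = 0.20 without it. A separate run with more precise sites (SE 0.10 to 0.35) at SD 0.3 gives 89.8% against 81.1% for 7 sites, and 85.6% against 73.4% for 3 sites.

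**Direction.** Under symmetric heterogeneity mean VE is unchanged (50.0% with and without the rule). If 15% of sites truly have low VE (SD 0.3), the rule raises mean pooled VE by about 2.2 to 2.6 points.

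**The case against.** The rule is prespecified and numeric, and both criteria must be met. The reason is to be investigated and documented, the all-sites sensitivity analysis is mandatory, and excluded sites stay visible in the plot. The SAP is generic guidance, due for update after the pilot season, and the figure is labelled as illustrative. All of this is true. It rules out ad hoc choice and makes exclusions visible, but it leaves the primary estimate selected on its result. The figure mismatch is editorial and affects no trial result.

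Three stronger readings are tempting and are not supported:

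- *The interval is always too narrow.* Overall coverage stays about nominal without true heterogeneity. Part of the shortfall at SD 0.2 and 0.4 is present with all sites kept and belongs to the Wald interval, which the fix below does not change.
- *The rule favours high VE.* It uses absolute values. The 6.6-point rise comes from artificial data with one low outlier, and a high outlier would move VE down. The protocol also says that EFPIA members have no access to the data.
- *The protocol's option on wide intervals does the same to pooling.* The sample size section says: "In case VE estimates with unacceptable large CIs are obtained, it might be considered to not report these estimates". This is optional and concerns reporting. It does not say that such estimates leave the pooled analysis, and the same paragraph says that smaller studies may still contribute to pooling. The lack of a threshold is a separate, minor selective-reporting point.

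**Conclusion.** The concern holds for section 3.4.3. Removing compliant sites on their own result understates between-site variance and makes the primary interval too narrow when sites truly differ, which is the situation the SAP's model assumes. The coverage attributable to the rule is about 3 to 4 points at SD 0.2 and roughly 7 to 10 points at SD 0.4, under the simulation assumptions above. Point estimates move whenever the rule is triggered, in either direction; a systematic bias needs outlying sites that lie mostly on one side. The recomputation of the SAP's example needs no outside assumption and establishes that the printed pooled line contradicts its footnote, so the example hides the effect of the rule.

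**What to change.** - Swap the roles of two analyses that are already planned. The primary meta-analysis keeps every protocol-compliant estimate, and the outlier and influence rule defines a sensitivity analysis. Amend sections 3.4.3 and 3.4.6 accordingly.
- Allow exclusion from the primary analysis only for a documented data or protocol error established without reference to the VE result.
- In Figure 1, correct either the pooled line (59.12, 48.29 to 67.68, I² 50.6% by REML if D(3) is left out) or the footnote. Under the revised rule the line can stand and the footnote should change.
- Name the τ² estimator: the printed result is REML, while the reference given in section 3.4.2 is for DerSimonian-Laird.
- Separately, in the protocol's sample size section, either commit to reporting all site estimates or fix a numeric criterion in advance that does not depend on the VE result, such as a minimum number of vaccinated subjects.

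The cost is SAP wording, one figure and one protocol sentence. The real downside is wider and less tidy pooled intervals when sites disagree.
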